4.2. Variable Definitions

4.2.1. Body Mass Index

Body mass index will be calculated as follows:

$$\text{BMI (kg/m}^2\text{)} = [\text{weight (kg)}] / [\text{height (m)}]^2.$$

4.2.2. Prior and Concomitant Medication

Prior medication is defined as any nonstudy medication started before the first dose of INCB050465.

Concomitant medication is defined as any nonstudy medication that is started accordingly:

- Before the date of first administration of INCB050465 and is ongoing throughout the study or ends on/after the date of first study drug administration.
- On/after the date of first administration of INCB050465 and is ongoing or ends during the course of study.

A prior medication could also be classified as "both prior and concomitant medication" if the end date is on or after first dose of INCB050465. In the listing, it will be indicated whether a medication is prior-only, concomitant-only, or both prior and concomitant medication.

For the purposes of analysis, all medications will be considered concomitant medications unless the medications can unequivocally be defined as not concomitant.

5. STATISTICAL METHODOLOGY

5.1. General Methodology

Unless otherwise noted, SAS[®] software (SAS Institute Inc, Cary, NC; v9 or later) will be used for the generation of all tables, graphs, and statistical analyses. Descriptive summaries for continuous variables will include, but not be limited to, the number of observations, mean, standard deviation, median, minimum, and maximum. Descriptive summaries for categorical variables will include the number and percentage of participants in each category.

Interim analyses are planned for this study as defined in Section 10.

5.2. Treatment Groups

This is a Phase 2, open-label, 2-cohort study. All analyses will be conducted independently for Cohort 1 and Cohort 2, and there will not be multiplicity adjustment between the cohorts. Within each cohort, there will not be any statistical comparison between the treatment groups.

For analysis purposes, the 20 mg once weekly dosing period and the 2.5 mg QD dosing period in Group A and Group B, respectively, are considered maintenance dosing periods. Within each of the 2 cohorts, data will be presented in summary tables by actual received treatment regimen and combined, with an exception for participants who cross over to the selected treatment regimen after the start of the maintenance dosing period.

For participants who cross over from the initially assigned treatment regimen to the selected treatment regimen, if the crossover happens on/prior to the start of the maintenance dosing period then the participant will be summarized, according to the actual received treatment, in the selected treatment regimen; otherwise, the participant will be summarized in:

- A separate treatment regimen (ie, Crossover) for the safety summaries during the maintenance dosing period (eg. summaries of TEAEs and exposure).
- The initially assigned treatment regimen for all other summaries.

Per Protocol Amendment (Version) 7, Cohort 1 was closed to further enrollment. If the number of participants who have enrolled in Cohort 1 is relatively few, summary tables will be replaced with listings.

5.3. Analysis Populations

5.3.1. All-Screened Population

The all-screened population includes all participants who signed the informed consent form. The all-screened population will be used for the summary of analysis populations.

5.3.2. Full Analysis Set

The FAS includes all participants enrolled in the study who received at least 1 dose of INCB050465.

The FAS will be used for the summary of demographics, baseline characteristics, participant disposition, and all efficacy data.

5.3.3. Safety Population

The safety population includes all enrolled participants who received at least 1 dose of INCB050465.

All safety analyses will be conducted using the safety population.

[REDACTED]

6. BASELINE, EXPOSURE, AND DISPOSITION VARIABLES AND ANALYSES

[Appendix A](#) provides a list of planned tables, figures, and listings. Sample data displays are included in a separate document.

6.1. Baseline and Demographics, Physical Characteristics, and Disease History

6.1.1. Demographics and Baseline Characteristics

The following demographics will be summarized and listed for the FAS: age, sex, race, ethnicity, geographic region, weight, height, and BMI. Eastern Cooperative Oncology Group performance status at baseline will be summarized and listed for the FAS.

6.1.2. Disease History

Time since diagnosis, initial cytogenetics/expression analysis, current cytogenetics/expression analysis, initial Ann Arbor stage, current Ann Arbor stage, initial presence of B-symptoms, current presence of B-symptoms, current MIPI risk category, bone marrow involvement (yes vs no), bulky disease at baseline (longest diameter ≥ 10 cm vs $5 < 10$ cm, vs < 5 cm) at baseline by the IRC, and relapsed/refractory status to the most recent prior therapy will be summarized and listed for all participants in the FAS. Date of tumor marker tests and test results will be listed.

Time since diagnosis will be calculated as:

$$\text{Time since diagnosis (years)} = (\text{Day 1 date} - \text{date of diagnosis} + 1) / 365.25.$$

6.1.3. Prior Therapy

Number of prior systemic cancer therapy regimens will be summarized for all participants in the FAS. The component drugs of prior systemic therapy regimens will be coded using the WHO Drug Dictionary. Number and percentage of participants with each drug will be summarized by WHO drug class and WHO drug PT. Regimen name, component drugs, start and stop date, route of the medication, best response, reason for discontinuation, and date of relapse/progression will be listed.

Number of participants who received prior radiation will be summarized for the FAS. Anatomical location of the administration, start and stop date, and total dose will be listed.

Number of participants who had prior surgery or surgical procedure for the cancer treatment will be summarized for the FAS. Date and description of the surgery/procedure will be listed.

Number of participants who had hematopoietic stem cell transplant will be summarized for the FAS. Date of transplant, type of transplant, source of cells, line of therapy, best response, date of relapse/progression, regimen name, and drug used with the transplant will be listed.

6.1.4. Medical History

Medical history will be coded to SOC and PT using MedDRA coding dictionary. For participants in the FAS, medical history will be summarized by SOC and PT and listed.

6.2. Disposition of Participants

The number and percentage of participants who were treated, who were ongoing with study treatment, who discontinued study treatment with a primary reason for discontinuation, who were still in the study, and who withdrew from the study with a primary reason for withdrawal will be summarized and listed for the FAS.

The number of participants enrolled by country and site will also be provided for the FAS.

6.3. Protocol Deviations

Protocol deviations recorded on the eCRF will be summarized and listed for the FAS.

6.4. Exposure

For participants in the safety population, exposure to INCB050465 will be summarized descriptively as the following:

- **Duration of treatment (days):** Date of last dose – date of first dose + 1.
- **Duration of treatment during the initial QD dosing period (days):** Date of last dose during initial QD dosing period – date of first dose + 1.
- **Duration of treatment during the maintenance dosing period (days):** Date of last dose – date of first dose during the maintenance dosing period + 1. Crossover participants who switched to the selected treatment regimen after the start of the maintenance dosing period will be summarized in a separate group (ie, Crossover).
- **Average reported daily dose during the initial QD dosing period (mg/day):** Total reported dose taken during initial QD dosing period (mg) / duration of treatment during the initial QD dosing period (days).
- **Average reported daily dose during the maintenance dosing period (mg/day):** Total reported dose taken during the maintenance dosing period (mg) / duration of treatment during the maintenance dosing period (days). Crossover participants who switched to the selected treatment regimen after the start of the maintenance dosing period will be summarized in a separate group (ie, Crossover).
- **Dose modifications:** Number of participants who had dose reduction and interruption will be summarized. The number of dose reductions and the number of interruptions for each participant will be summarized.

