• Any recurrent Grade 3 toxicity after 2 dose reductions.	Discontinue INCB050465 administration and follow-up per Protocol. Exceptions require approval of sponsor.
• Any other Grade 4 toxicity.	Discontinue INCB050465 administration and follow-up per Protocol. Exceptions require approval of sponsor.

ALT = alanine aminotransferase; AST = aspartate aminotransferase; CMV = cytomegalovirus; IV = intravenous; ULN = upper limit of normal.

Table 4: Dose Levels and Reductions for INCB050465

Timepoint	Treatment A	Treatment B
Starting dose	20 mg QD for 8 weeks (Day 1 through Day 56)	20 mg QD for 8 weeks (Day 1 through Day 56)
First dose reduction	10 mg QD	10 mg QD
Second dose reduction	5 mg QD	5 mg QD
Week 9 (Day 57) onward	20 mg once weekly ^a	2.5 mg QD ^b
First dose reduction	10 mg once weekly	1 mg QD ^c
Second dose reduction	5 mg once weekly	NA

^a All subjects will receive 20 mg once weekly at Week 9 (Day 57) regardless of prior dose level, unless a dose modification of a switch to a QW schedule before Week 9 is required for diarrhea/colitis management (see Table 5).

^b All subjects will receive 2.5 mg QD at Week 9 (Day 57) regardless of prior dose level, unless a dose modification of a switch to a QW schedule is required for diarrhea/colitis management (see Table 5).

^c Further dose modification due to diarrhea or colitis for subjects on 1 mg QD is permitted (see Table 5).

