
 • Diarrhea (≥ Grade 3). • Noninfectious colitis (any grade; confirmed or suspected). 	
Step 1: Interrupt INCB050465. Perform work-up for infection (including CMV, C. difficile, etc) immediately. Initiate or continue supportive care (see Section 5.4.2). Consider colonoscopy with biopsy for diarrhea ≥ Grade 3 and/or if symptoms^a suggestive of colitis. Monitor every 48 hours until resolution.
 
Step 2: If infection* is ruled out, start oral steroids, or consider IV steroids if participant is being given IV fluids. If no improvement with oral steroids within 48 hours, switch to IV steroids.
 
*For infectious diarrhea/colitis, follow institutional standard of care guidelines and restart pascalisib according to clinical judgement after resolved to ≤ Grade 1. Consult with medical monitor if needed.
 
Step 3: When diarrhea/colitis resolves to ≤ Grade 1, continue supportive care and taper steroids according to institutional standard of care. When taper is complete (eg, no steroid or ≤ 10 mg/day prednisone or equivalent) and diarrhea/colitis is ≤ Grade 1, restart INCB050465 as described herein and with approval of the medical monitor. Continue to monitor.
 
  
 INCB050465 Current Dose	Dose Modification	
   
 Any dose with QD dosing	20 mg QW regardless of Treatment A or B assignment	
 
 20 or 10 mg QW	Restart next lower dose	
 
 5 mg QW	Permanently discontinue	
  
 
Step 4: If ≥ Grade 3 diarrhea/colitis (any grade) reoccurs, permanently discontinue INCB050465.
	INCB050465 Current Dose	Dose Modification	Any dose with QD dosing	20 mg QW regardless of Treatment A or B assignment	20 or 10 mg QW	Restart next lower dose	5 mg QW	Permanently discontinue
INCB050465 Current Dose	Dose Modification								
Any dose with QD dosing	20 mg QW regardless of Treatment A or B assignment								
20 or 10 mg QW	Restart next lower dose								
5 mg QW	Permanently discontinue								

^a Diarrhea accompanied by abdominal pain and/or mucus or blood in stool.

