To better understand the safety and efficacy of INCB050465, a total of 70 additional participants (30 participants in Cohort 1 and 40 participants in Cohort 2) will be enrolled into 1 of the 2 treatment regimens being evaluated in this study. The treatment regimen will be selected after enrollment is completed for either Cohort 1 or Cohort 2 (ie, 60 participants enrolled) and after evaluation of emerging safety and efficacy data from this and other monotherapy studies of INCB050465 in non-Hodgkin lymphoma. Once a treatment regimen is selected, the nonselected treatment regimen will be closed to further enrollment. Participants receiving the nonselected treatment regimen may switch to the selected treatment regimen or remain on their current treatment regimen, provided they have not met study-treatment withdrawal criteria and there are no safety concerns for their current treatment regimen. There will be no rebaselining for participants who switch treatment regimens and all participants will continue to follow the same assessment schedule.

Participants will receive treatment until disease progression, death, unacceptable toxicity, or consent withdrawal, whichever occurs first. Participants will be evaluated for ORR by an IRC and followed for DOR, PFS, and OS.

Figure 1: Study Design of INCB 50465-205

EOT = end of treatment; MCL = mantle cell lymphoma; QD = once daily

^a A futility analysis will be performed for each of the cohorts when the first 30 patients in each cohort have been treated and evaluated for response (see Section 9.6). Final analysis will occur when all subjects in the respective Cohort have received at least 1 postbaseline disease assessment, or have progressed, withdrawn from the study, or died.

^b Cohort 1 will be closed to further enrollment by Protocol Amendment 7 with approximately 50 subjects enrolled.

^c Subjects who discontinue study treatment for a reason other than disease progression will continue with disease assessments by radiologic imaging per the Schedule of Assessments.

^d Every 12 weeks by clinic visit, telephone, or e-mail.

^e Urine pregnancy and dispensing of study treatment will occur every 4 weeks.

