2.4.2	Summary of Best Overall Response and Objective/Complete Response Rate as Reported by Investigator – Crossover as a Separate Treatment Group	FAS	
2.4.3	Summary of Best Overall Response as Determined by Independent Review Committee for Crossover Participants	FAS	
2.4.4	Summary of Best Overall Response as Reported by Investigator for Crossover Participants	FAS	
2.4.5	Summary of Duration of Response as Determined by Independent Review Committee – Censoring Crossover Participants	FAS	
2.4.6	Summary of Duration of Response as Reported by Investigator – Censoring Crossover Participants	FAS	
2.4.7	Summary of Progression-Free Survival as Determined by Independent Review Committee – Censoring Crossover Participants	FAS	
2.4.8	Summary of Progression-Free Survival as Reported by Investigator – Censoring Crossover Participants	FAS	
Safety			
3.1.1	Summary of Exposure and Compliance	Safety	
3.1.2	Summary of Exposure and Average Daily Dose During Initial QD Dosing Period	Safety	
3.1.3	Summary of Exposure and Average Daily Dose During Maintenance Dosing Period	Safety	
3.2.1	Overall Summary of Treatment-Emergent Adverse Events	Safety	X
3.2.2	Summary of Treatment-Emergent Adverse Events by MedDRA System Organ Class and Preferred Term	Safety	X
3.2.3	Summary of Treatment-Emergent Adverse Events by MedDRA Preferred Term in Decreasing Order of Frequency	Safety	X
3.2.4	Summary of Treatment-Emergent Adverse Events by MedDRA System Organ Class, Preferred Term, and Maximum Severity	Safety	X
3.2.6	Summary of Grade 3 or Higher Treatment-Emergent Adverse Events by MedDRA System Organ Class and Preferred Term	Safety	X

Table No.	Title	Population	Standard
3.2.7	Summary of Grade 3 or Higher Treatment-Emergent Adverse Events by MedDRA Preferred Term in Decreasing Order of Frequency	Safety	X
3.2.8	Summary of Serious Treatment-Emergent Adverse Events by MedDRA System Organ Class and Preferred Term	Safety	X
3.2.9	Summary of Serious Treatment-Emergent Adverse Events by MedDRA Preferred Term in Decreasing Order of Frequency	Safety	X
3.2.10	Summary of Treatment-Related Treatment-Emergent Adverse Events by MedDRA System Organ Class and Preferred Term	Safety	X
3.2.11	Summary of Treatment-Related Treatment-Emergent Adverse Events by MedDRA Preferred Term in Decreasing Order of Frequency	Safety	X
3.2.12	Summary of Treatment-Related Treatment-Emergent Adverse Events by MedDRA System Organ Class, Preferred Term, and Maximum Severity	Safety	X

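### SAP 6.4 uses the same first-to-last-dose + 1 denominator for weekly and daily maintenance, so mg/day in Table 3.1.3 reads high when a period ends on weekly dosing, markedly so for short exposure

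*SAP*

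**What the plan says.** SAP 6.4 (Exposure) defines the duration of treatment in maintenance as the date of last dose minus the "date of first dose during the maintenance dosing period + 1". The average reported daily dose in maintenance is then "Total reported dose taken during the maintenance dosing period (mg) / duration of treatment during the maintenance dosing period (days"). Neither definition distinguishes weekly from daily dosing. The only special case is that participants who cross over after maintenance has started are shown as a separate Crossover group.

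SAP 5.2 (Treatment Groups) names "the 20 mg once weekly dosing period and the 2.5 mg QD dosing period in Group A and Group B, respectively" as maintenance dosing periods and presents data by regimen received and combined. The 6.4 formula therefore applies to weekly dosing by the plan's own terms. The result goes into Appendix A, Table 3.1.3, "Summary of Exposure and Average Daily Dose During Maintenance Dosing Period".

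Weekly dosing can enter that table in two ways:
- **Treatment A.** SAP 3 says "Once a treatment regimen is selected, the nonselected treatment regimen will be closed to further enrollment", but participants already on that regimen may remain on it. SAP 11.2 records that Group B was the selected one.
- **The switch for diarrhea/colitis.** Protocol Table 4 sets 2.5 mg QD for Treatment B from "Week 9 (Day 57) onward", "unless a dose modification of a switch to a QW schedule is required for diarrhea/colitis management". Protocol Table 5 gives the modified schedule for any QD dose as "20 mg QW regardless of Treatment A or B assignment". A Group B participant can therefore also finish on weekly doses.

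**The concern.** Dividing total mg by days is a fair daily average only if each dose is matched with the days it is meant to cover. Adding 1 to first-to-last-dose time does this for daily dosing, because the last dose covers one day. A weekly dose covers seven, so + 1 drops the last six days of the final interval while keeping its full 20 mg in the numerator.

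Table 3.1.3 would then set a weekly column that is biased upward beside a QD column that is not. The scheduled rates are close: 20/7 = 2.86 against 2.5 mg/day, a ratio of 1.14. An artefact of similar size in one column could be read as a real difference in dose intensity. At stake is the reading of one descriptive table.

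**Working it through.** The plan states no average-dose figure, so there is nothing to reproduce. The formula was checked first on daily dosing and then applied to weekly dosing.

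**Inputs.** Denominator: last dose - first maintenance dose + 1 (SAP 6.4). Weekly regimen: 20 mg every 7 days. Daily regimen: 2.5 mg every day (both SAP 3).

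**Daily check.** 84 consecutive doses of 2.5 mg: 210 mg / 84 days = 2.5 mg/day. The formula is exact.

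**Weekly dosing, on schedule, k weekly slots.**
- Days from first to last dose, + 1: 7(k-1) + 1 = 7k - 6
- SAP result: 20k/(7k-6) mg/day
- Each dose credited with its own interval: 20k/(7k) = 2.86 mg/day
- Ratio: 7k/(7k-6); excess over the scheduled rate: 6/(7k-6)

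| k | SAP denominator (days) | SAP mg/day | Ratio to 2.86 |
|---|---|---|---|
| 1 | 1 | 20.0 | 7.0 |
| 2 | 8 | 5.0 | 1.75 |
| 4 | 22 | 3.64 | 1.27 |
| 8 | 50 | 3.20 | 1.12 |
| 12 | 78 | 3.08 | 1.08 |
| 26 | 176 | 2.95 | 1.03 |
| 52 | 358 | 2.91 | 1.017 |

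The excess falls below 10% from k = 10 and below 5% from k = 19. The ratio is the same for a reduced weekly dose if that dose is constant.

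**Missed doses.** Here k is the number of weekly slots spanned, not doses taken. With 11 doses over 12 slots, the SAP gives 220/78 = 2.82 and the interval-based value is 220/84 = 2.62. The ratio is 84/78 = 1.077.

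**Who is affected.** Treatment A participants who stay on weekly maintenance, and anyone whose last doses are weekly after the Table 4/Table 5 switch. Participants on uninterrupted QD maintenance, and those who move from A to B and end on QD dosing, do not lose the six days.

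**With + 7.** The denominator becomes 7k, and the result is 20/7 = 2.86 for every untruncated on-schedule k.

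**The case against.** **It is a definition, applied consistently.** The SAP defines a reported average over first-to-last-dose time and sets no target of 2.86 mg/day. Crediting the last weekly dose with seven days is this review's benchmark. That is fair, and first-to-last-dose time is acceptable as a measure of duration. As a mg/day denominator it still fails: one weekly dose would be reported as 20 mg/day, the same as the initial daily dose.

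**The consequence is small.** No comparison between regimens is tested (SAP 3.2 and 5.2). Compliance in SAP 6.5 does not use duration. The main affected column is the non-selected regimen, and the excess is 1.7% at 52 slots. All of this stands, and it limits the point to a minor one.

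**A reader might infer that the Treatment A mean is badly inflated.** The documents do not support a figure. Assuming a constant weekly stopping rate with a mean of 53, 26 or 12 weekly doses gives mean ratios of 1.17, 1.33 and 1.67, but participants with a single weekly dose dominate them. Without those participants the range is 1.06 to 1.18. The ratio at the median number of doses is 1.02, 1.05 and 1.12. Only the 53 has a link to the documents, and a loose one: the Protocol Synopsis expects about 14 months of treatment, and (14 x 30.44 - 56)/7 = 52.9. The means of 26 and 12 are pure assumptions.

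**A reader might also infer that the Group B column is materially wrong.** It can contain affected participants, but Protocol Table 5 requires interruption, and completion of any steroid taper, before the weekly restart, which lengthens the denominator and dilutes the error. Take 28 days of QD maintenance followed by one weekly dose. The ratio is 35/29 = 1.21 with no pause, 49/43 = 1.14 with an assumed 14-day pause and 63/57 = 1.11 with an assumed 28-day pause. How many participants make the switch is not given.

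**Conclusion.** The point holds as a minor defect in a stated rule. For periods that end on weekly dosing, SAP 6.4 yields 7k/(7k-6) times the scheduled mg/day. This assumes on-schedule slots, a constant dose, and a final dose that covers its full seven days; death or a change of regimen within six days of it would shorten the correction.

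The error is large for a participant who stops after one or a few weekly doses and small for long exposure. The size of any shift in a group mean cannot be derived from the documents.

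It would be going too far to conclude that regimen selection, efficacy, TEAE percentages or compliance are compromised: none of the planned analyses of these uses this quantity. SAP 6.4 also does not say to which period a Group B participant's weekly doses before Week 9 belong. That is missing detail, separate from this error.

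**What to change.** In SAP 6.4, for the average daily dose of a period that ends on once-weekly dosing, define the denominator as last dose date - first dose date of that period + 7. Truncate it at death and at the day before the first dose of the next period or regimen, so that no day is counted twice. Keep + 1 for periods that end on QD dosing, and keep the existing definition of duration of treatment. Add a footnote to Table 3.1.3 that the mg/day denominator differs from the displayed duration.

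The cost is a short addition to the SAP, a modest programming change (a participant-level flag for periods that end on weekly dosing, plus the truncation) and the footnote. One small downside remains: for participants still on weekly dosing at data cutoff, the denominator may include up to 6 days not yet observed. Results for uninterrupted QD dosing do not change, and no dose or clinical rule is touched.
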